Study Protocol and Statistical Analysis Plan for NCT03750968

Lutein & Zeaxanthin in Pregnancy – Carotenoid Supplementation during Pregnancy: Ocular and Systemic Effects

The following pages contain the IRB approved study protocol and statistical analysis plan at the most recent renewal approved on 21 December 2022.

Date: Tuesday, May 2, 2023 2:01:03 PM

[Print](#)
[Close](#)
IRB_00116610
Created: 10/1/2018 12:13 PM

IRB_00116610

1. Contacts and Title

PI: [name]

Submitted: 11/21/2018

Title: Lutein & Zeaxanthin in Pregnancy (L-ZIP) - Carotenoid Supplementation During Pregnancy: Ocular and Systemic Effects

1. Study Introduction

1. Responsible Investigator:

[name]

Email	Training	Col Date
[contact]	7/27/2021 MCG	4/3/2023

a. Position of the Investigator:

- Faculty or Non-Academic Equivalent
- Student
- Staff
- Resident/Fellow
- Other

2. Contact Persons for the Responsible Investigator:

Name	Email	Training
[name]	[contact]	1/30/2023 MCG
[name]	[contact]	CG
[name]	[contact]	1/31/2023 MCG
[name]	[contact]	1/4/2023 MCG
[name]	[contact]	6/17/2022 MCG

3. Guests of the Responsible Investigator:

Last Name	First Name	E-Mail
-----------	------------	--------

There are no items to display

4. What type of application is being submitted?

[New Study Application](#) (or Amendment/Continuing Review)

5. Title Of Study:

Lutein & Zeaxanthin in Pregnancy (L-ZIP) - Carotenoid Supplementation During Pregnancy: Ocular and Systemic Effects

6. Study Purposes and Objectives:

The primary objective of this study is to characterize the carotenoid status of mothers during pregnancy, specifically to determine if prenatal supplementation counteracts maternal systemic and ocular carotenoid depletion.

The primary outcome measure will be change in carotenoid levels from enrollment to final study visit (birth of child) as measured in serum, skin and the macula by high-performance liquid chromatography (HPLC), resonance Raman spectroscopy, and macular pigment imaging, respectively.

7. Is this a multi-site study, where more than one site needs IRB approval?

Yes No

8. Background and Introduction:

The human macula has a high concentration of the dietary carotenoids lutein and zeaxanthin which results in a yellow spot centered on the fovea, the *macula lutea*. Carotenoids are abundant in plants, fruits, and vegetables, and they are thought to play important roles in the physiologic function of the retina and other tissues (Scott et al., 1996; Scarmo et al., 2010; Zimmer et al., 2007; [name] et al., 2016). Of the hundreds of carotenoids found in nature, 10 to 15 are detectable in human serum, but only lutein, zeaxanthin, and their metabolites are present in the retina (Bone et al., 1985; Khachik et al., 1997). The potential antioxidant and photoprotective effects of carotenoids, especially with regard to age-related macular degeneration (AMD), have been studied extensively in the laboratory and in clinical studies (Seddon et al., 1994; [name] et al., 2002; Eye Disease Case-Control Study Group, 1993), and recent reports have demonstrated a role of dietary and supplemental carotenoids in slowing or preventing AMD (Age-Related Eye Disease Study (AREDS) Report No. 22, 2007; AREDS2 Report No. 3, 2014).

Studies also suggest a functional role for the macular carotenoid pigment earlier in life, at a time when they may enhance contrast sensitivity, decrease glare disability, and even increase visual acuity (Kvansakul et al., 2006; Stringham et al., 2008; Olmedilla et al., 2003). The physiological accumulation of the macular carotenoid pigments occurs even *in utero* (Malone, 1975; Dimentstein et al., 1996). Investigators have recently shown that the macular pigment is detectable immediately after birth, correlates with infant and maternal serum zeaxanthin levels, and progressively increases through the first seven years of life ([name] et al., 2013). This suggests that the macular carotenoids play physiological and protective roles throughout the lifecycle and may be particularly important during infant visual development.

Prenatal vitamin and micronutrient supplementation is standard-of-care for pregnant women worldwide; however, with the exception of a few ingredients, most prenatal supplementation guidelines are not yet supported by substantial prospective clinical research. Recently, prenatal supplements with added lutein and zeaxanthin have entered the American market with the stated intentions of enhancing infant visual and neural development and maintaining maternal health. Although clinical trials were never performed to support these contentions, it is physiologically plausible from the neonate's perspective because these dietary carotenoids are selectively concentrated in human ocular and neural tissue *in utero*, especially during the third trimester of pregnancy.

From the mother's perspective, the last trimester of pregnancy is a time when she must transfer some of her carotenoid stores to the developing infant via the placenta, potentially putting her at risk for depletion systemically and in her ocular tissues. On review of the published literature, there are conflicting data regarding systemic maternal carotenoid status throughout pregnancy, and absolutely nothing is known about maternal macular pigment levels in the eye during pregnancy. Some, but not all, studies report lower serum carotenoid levels in pregnant women. [name] and others (Henriksen et al., 2013; Kiely et al., 1999; Zhang et al., 2001) have reported that mothers who did not take lutein or zeaxanthin supplements during pregnancy had >50% reductions of serum lutein and zeaxanthin concentrations and ~20% lower total skin carotenoids at the time of delivery when compared to our clinic's average of unsupplemented non-pregnant adults.

Prospective, controlled clinical trials to demonstrate the benefits of carotenoid supplementation during pregnancy have never been conducted. To obtain data relative to the feasibility of such trials, this study will be a comprehensive, prospective assessment of prenatal lutein + zeaxanthin supplementation on maternal and infant ocular and systemic biomarkers of carotenoid status throughout pregnancy.

Please see pp. 27- 30 of the protocol for the list of literature cited.

IRB_00116610

Created: 10/1/2018 12:13
PM

IRB_00116610

2. Study Location and Sponsors

PI: [name]

Submitted: 11/21/2018

Title: Lutein & Zeaxanthin in Pregnancy (L-ZIP) -
Carotenoid Supplementation During Pregnancy:
Ocular and Systemic Effects

2. Study Location and Sponsors

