Initial evaluation of each mother's carotenoid status will be obtained prior to starting any study supplements. Subsequent evaluations while participants are taking the study supplements will be performed in conjunction with routine prenatal visits to their Obstetrician, at approximately 22-26 weeks gestational age and again at 37-39 weeks gestational age. All mothers will undergo a final assessment within two weeks of giving birth.

Infants' evaluations will be performed in the first two weeks of life, either during the original hospital stay or at a follow up outpatient clinic visit.

Visit:	Screening/ Baseline	Maternal Supplementation		
	T1	T2	T3	Birth
Timeframe:	Before 14 Wks GA	22-26 Wks GA	37-39 Wks GA	0 to 2 Wks
Informed Consent	X			
Randomization	X			
Maternal visual acuity and contrast sensitivity	X	X	X	X
Maternal nutritional surveys	X	X	X	X
Dilated eye examination	X			
Maternal serum carotenoids	X	X	X	X
Maternal macular pigment imaging	X	X	X	X
Maternal skin carotenoids	X	X	X	X
Dispense prenatal supplement and do pill counts	X	X	X	X
Infant cord blood carotenoids				X
Infant macular pigment imaging				X
Infant foveal imaging (sdOCT)				X
Infant skin carotenoids				X

Unscheduled Visits

Mothers may be seen for Unscheduled Visits if deemed necessary for repeat measurements or follow-up of Adverse Events. If a mother delivers her baby prematurely, she and her infant will remain in the study and will be asked to complete the final study visit.

Description of Study Assessments:

Visual Function - Manifest refraction, and measurement of best-corrected visual acuity and contrast sensitivity of the mothers will be obtained by certified ophthalmic technicians using standardized protocols. The study staff performing visual acuity will be masked to the treatment assignment. Best-corrected visual acuity testing will be assessed on ETDRS back-lit charts starting at a distance of 4 m, and should precede any examination requiring administration of eye drops to dilate the eye or any examination requiring contact with the eye. Contrast sensitivity will be measured by the Pelli-Robson threshold contrast sensitivity chart at 1 m.

Maternal Eye Exam - The complete ophthalmic exam will consist of the following:

- External examination of the eye and adnexa.
- Routine screening for eyelids/pupil responsiveness (including ptosis, abnormal pupil shape, unequal pupils, abnormal reaction to light and afferent pupillary defect).

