Statistical power and sample size (N) for one of the primary outcome measures, maternal skin carotenoids at birth, was determined using data from the previous study by Henriksen et al. (2013) in which the average maternal skin carotenoids \pm SD at birth was 34000 ± 8300 . This value is 20% lower than the University of Utah Moran Eye Center clinic average value of $\sim 42,500$ Raman counts reported for the ancillary AREDS2 study ([name] et al., 2012). With power of 0.90 and alpha 0.05, a sample size of 20 was calculated for each group in order to detect and prevent a 20% decline during pregnancy. In order to accommodate subsequent ineligibility due to premature birth, low birth weight, or other problems ($\sim 10\%$) and to plan for expected noncompliance and loss to follow up ($\sim 20\%$), we intend to enroll 30 subjects in the Carotenoid Supplementation Group and another 30 in the Control Group.

The other outcome measures (maternal ocular carotenoid depletion during pregnancy, infant carotenoid status at birth, and the exploratory outcome measures of foveal maturity at birth and visual function changes during pregnancy) are not as well characterized, but we estimate that a similar sample size of 20 patients per group will be sufficient to detect differences in these indices.

Statistical Analysis Sets

The Intent-to-Treat set will include all randomized subjects who complete the Baseline Visit carotenoid status evaluations and receive study supplements. Subjects will be analyzed by the supplement arm assigned at the Baseline Visit.

A modified Intent-to-Treat set will include all randomized subjects who receive investigational product and complete carotenoid evaluations for at least one trimester study visit while utilizing study supplements.

Efficacy Analyses

The primary, secondary and exploratory efficacy analyses will be performed using the modified Intent-to-Treat subject set. Paired t-tests will compare the carotenoid status at enrollment and at the final study visit of the mothers receiving carotenoid supplementation to mothers not receiving carotenoid supplementation. We will also compare carotenoid status of infants whose mothers received carotenoid supplementation to infants of mothers without carotenoid supplementation. Significance will be set at 2-tailed $P < 0.05$. The associations between maternal and infant carotenoid status will be assessed with regression analysis.

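### The maternal comparison uses the enrollment value only by subtraction; adjusting for it would gain precision and remove the effect of chance baseline imbalance at almost no cost

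*Combined protocol and SAP*

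**What the plan says.** Study Introduction, item 6 (Study Purposes and Objectives) sets the maternal endpoint: "The primary outcome measure will be change in carotenoid levels from enrollment to final study visit (birth of child"), measured in serum, skin and macula.

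Study Information, item 9 (Efficacy Analyses) gives the test: "Paired t-tests will compare the carotenoid status at enrollment and at the final study visit of the mothers receiving carotenoid supplementation", set against mothers who do not receive it, at two-sided 0.05. Regression is mentioned only for the association between mother and infant. Diet and BMI appear only as subgroup factors. No covariate is named for the comparison of arms.

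Study Information, item 6 (Study Visit Schedule) shows that the covariate will exist: "Initial evaluation of each mother's carotenoid status will be obtained prior to starting any study supplements". The visit table lists serum, skin and macular measures at T1.

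The sample size section works on a different quantity: "Statistical power and sample size (N) for one of the primary outcome measures, maternal skin carotenoids at birth". It uses a birth mean of 34,000 with SD 8,300 and a clinic average of about 42,500, and concludes: "With power of 0.90 and alpha 0.05, a sample size of 20 was calculated for each group".

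**The concern.** Subtracting the enrollment value is the same as adjusting for it with a slope fixed at 1. In two correlated measurements with equal SDs the true slope is rho, which is below 1. Two things follow.

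- **Lost precision.** The change score carries baseline noise that a fitted slope would remove. If rho is below 0.5 (with equal SDs), change is noisier than the birth value for which the trial was sized.
- **Conditional bias.** If one arm happens to start higher, the change score over-corrects through regression to the mean and pulls that arm's estimate down. The estimate is unbiased over repeated randomizations, but not given the imbalance actually seen.

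With about 20 evaluable mothers per arm, both matter. The planned power does not carry over to a raw change analysis unless rho is at least about 0.5, and the documents give no value for it.

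**Working it through.** **Inputs from the sample size section.** SD at birth 8,300; difference 42,500 − 34,000 = 8,500 (20% of 42,500); power 0.90; alpha 0.05; 20 per arm evaluable, 30 enrolled. The two-sided test comes from Efficacy Analyses.

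**Assumptions.** The correlation rho between enrollment and birth is not given, so it is varied. The SD is taken as 8,300 at both visits and in both arms.

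**1. The plan's own figure.** For a two-sample comparison of birth values:

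n per arm = 2 × [8,300 × (1.960 + 1.282) / 8,500]² = 20.04

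This matches the stated 20, apart from rounding up. Power at 20 per arm is 0.899 by the normal approximation and 0.884 by the t distribution. So the 20 belongs to an unadjusted comparison of levels at birth, not of changes.

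**2. SD under each analysis.**

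- Change: 8,300 × √(2(1 − rho))
- ANCOVA: 8,300 × √(1 − rho²)
- Variance ratio, ANCOVA to change: (1 − rho²) / [2(1 − rho)] = (1 + rho)/2

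Estimating the slope with 40 mothers multiplies the ANCOVA variance by about 1 + 1/36.

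**3. Power at 20 per arm, difference 8,500 (t-based).**

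| rho | SD, change | SD, ANCOVA | Variance ratio | Ratio with slope cost | Power, change | Power, ANCOVA | Power, ANCOVA with slope cost |
|---|---|---|---|---|---|---|---|
| 0.3 | 9,821 | 7,918 | 0.65 | 0.67 | 0.760 | 0.911 | 0.903 |
| 0.5 | 8,300 | 7,188 | 0.75 | 0.77 | 0.884 | 0.954 | 0.949 |
| 0.7 | 6,429 | 5,927 | 0.85 | 0.87 | 0.983 | 0.993 | 0.992 |
| 0.9 | 3,712 | 3,618 | 0.95 | 0.98 | about 1.00 | about 1.00 | about 1.00 |

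Mothers per arm needed for 0.90 power (normal approximation), change against ANCOVA: 29 v 19 at rho 0.3, 21 v 16 at 0.5, 13 v 11 at 0.7.

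At the extreme of rho = 0, change has power 0.61, and ANCOVA has 0.875 after the slope cost. At rho 0.95 the variance ratio with slope cost is 1.002, so adjustment neither helps nor harms.

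**4. Chance imbalance at enrollment.** The standard error of the baseline difference is 8,300 × √(2/20) = 2,625 counts. An imbalance of one standard error shifts the change estimate, in the opposite direction, by (1 − rho) × 2,625:

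| rho | Shift (counts) | Share of 8,500 |
|---|---|---|
| 0.3 | 1,837 | 22% |
| 0.5 | 1,312 | 15% |
| 0.7 | 787 | 9% |
| 0.9 | 262 | 3% |

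**5. Check by simulation (8,000 trials per rho).** The slope of the change estimate on the baseline imbalance was −0.69, −0.51, −0.31 and −0.09 at rho 0.3, 0.5, 0.7 and 0.9, in line with −(1 − rho). For ANCOVA it was about zero throughout. Simulated power at rho 0.3, 0.5 and 0.7 was 0.76, 0.89 and 0.98 for change and 0.91, 0.95 and 0.99 for ANCOVA.

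**The case against.** The strongest reply is that the size of the gain rests on quantities the documents do not supply.

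- **Correlation.** At rho 0.5 a change analysis has the same power, 0.884, as the birth-level test the trial was sized on. Above that it does better, and at 0.7 the two methods are nearly level. The protocol describes the macular measure as highly reproducible and repeats each skin reading three times, which may point to a higher rho. Neither fact fixes rho across a pregnancy.
- **Equal SDs.** If the enrollment SD were 80% of the birth SD, the variance ratio before slope cost would be (1 − 0.49)/(1 + 0.64 − 2 × 0.7 × 0.8) = 0.51/0.52 = 0.98 at rho 0.7, and 0.36/0.36 = 1.00 at rho 0.8. A larger enrollment SD would favor ANCOVA more.
- **Number of mothers.** Twenty per arm is the planned floor. The modified intent-to-treat set does not exclude noncompliers, and preterm deliveries stay in the study. At 24 per arm, power for change against ANCOVA (before slope cost) is 0.84 v 0.95 at rho 0.3 and 0.94 v 0.98 at rho 0.5.
- **Scope.** The figures concern skin only; nothing here sizes the gain for serum or macula.
- **Deferred plan.** A complete analysis plan is promised before database lock and could add the adjustment.

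These points stand as limits on the size. They do not reverse the direction: apart from the small slope cost, ANCOVA is never less precise than change or the final value alone. Not knowing rho is a reason to use the method that does not depend on it. The text on the deferred plan promises statistical methods but does not commit to baseline adjustment.

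It is also fair to say that a paired t-test compares visits within an arm, so the plan does not clearly state any between-arm test. The same model would repair both problems.

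**Conclusion.** The concern holds. The enrollment value is collected before supplementation on all three primary scales, yet it enters the maternal comparison only by subtraction. For skin, assuming equal SDs of 8,300 and 20 mothers per arm, adjustment reduces variance by 35%, 25% and 15% at rho 0.3, 0.5 and 0.7 (33%, 23% and 13% after the slope cost). The clearest consequence is at low rho, where raw change falls well short of the planned 0.90 power and ANCOVA stays close to it.

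The direction is firm, but the size is not, because rho and the enrollment SD are assumptions. The issue is efficiency and conditional bias, not validity: the trial remains interpretable without the change, and the stated sample size is not wrong for the quantity it was computed on. The change should be made, because the possible benefit is material and the cost is close to nil.

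**What to change.** In Efficacy Analyses, state that each maternal measure (serum, skin, macula) will be compared between arms by a linear model of the final-visit value on arm and the T1 value of the same measure. Report the adjusted difference with its 95% confidence interval. Keep within-arm changes as description only.

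The endpoint in Study Purposes and Objectives can remain a change. Modeling the change with the T1 value as covariate gives the same arm effect as modeling the final value. A cross-reference there to the adjusted model would keep the two sections aligned.

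T1 dietary lutein and zeaxanthin intake and T1 BMI may be added if named in advance, but the fix does not depend on them.

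The cost is one or two sentences in the analysis plan and one degree of freedom per covariate. It needs no new data and no additional mothers.

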Participation in these procedures is optional and participants may decline any or all of them and still participate in the main study. Participant identifiers will be stored separately from the banked samples and participants will be able to withdraw their samples if they so desire.

Banked samples may be shared with other researchers, who must have IRB approval for their use and material/data transfer agreements with the University of Utah as applicable.

7. Are all procedures for research purposes only (non-standard or non-standard of care procedures)?

Yes No

If no, list the procedures that are performed for research purposes only (non-standard or non-standard of care procedures):

All Protocol-specified procedures are for research purposes only, with the exception of dispensing prenatal supplements. Expectant mothers will be taking prenatal supplements whether or not they agree to participate in this study.

8. Is there a safety monitoring plan for this study?

Yes No

9. Provide a summary of the statistical methods, data analysis, or data interpretation planned for this study. Factors for determining the proposed sample size (e.g., power) should be stated.

Statistical Analysis

The study outcome data will be analyzed by a consultant from the University of Utah Study Design and Biostatistics Center of the Center for Clinical and Translational Science.

Image analysis of retinal camera macular pigment measures will be conducted in [name] laboratory. Foveal anatomy parameters such as width, depth, and layer structure will be assessed by Drs. [name] and [name] using methods based on previously published protocols.

Sample Size Calculation and Power Considerations

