Subgroup analyses will be performed to assess the influences of maternal dietary carotenoid intake, compliance with study supplement use, co-existing medical conditions, BMI, infant gender, and other factors on our study results, with proper attention to the effects of multiple tests on the ability to draw conclusions.

The complete statistical analysis plan will be finalized prior to database lock, and will provide statistical methods as well as descriptions of how missing, unused and spurious data will be addressed. Summarization of study data will be prepared of subject demographics, baseline characteristics, and investigational product exposure.

Safety Analyses

Serious and unexpected adverse events will be collected from the time of the first study supplement administration until a subject completes the study or discontinues prematurely. Treatment emergent adverse events (TEAEs) are defined as those AEs that develop or worsen after the first dose of study supplement and up to 30 days beyond the last dose of study medication. The current version of MedDRA will be used to classify all AEs.

Treatment- emergent adverse events will be summarized by System Organ Class and Preferred Term, in accordance with the MedDRA coding dictionary. The number of subjects reporting each AE preferred term will be tabulated for all TEAEs and separately for those considered as related to study treatment by the Principal Investigator. The number of subjects reporting SAEs will also be tabulated. Adverse event summaries will be presented for each treatment group separately.

Adverse events will be summarized by MedDRA coding terms, and separate tabulations also will be produced for related adverse events (those considered by the Investigator as definitively drug related), serious adverse events and discontinuations due to adverse events. Findings from ophthalmologic examinations will be tabulated for changes over time on study. Separate summaries will be prepared for systemic (non-ocular) and ocular AEs, with events in the study eye and non-study eye summarized separately.

Title: Lutein & Zeaxanthin in Pregnancy (L-ZIP) - Carotenoid Supplementation During Pregnancy: Ocular and Systemic Effects

Consent Process

1. The following investigators and internal staff will obtain consent (as indicated on the Study Location and Sponsors Page):

[name]	University of Utah
[name]	University of Utah
[name]	University of Utah
[name]	University of Utah

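### Serum, skin and macula are named primary without ranking at an unsplit two-sided 0.05; separate claims would carry about 8–14% family-wise error, and the macula's primary status is not consistent

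*Combined protocol and SAP*

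**What the plan says.** Study Introduction, item 6 (Study Purposes and Objectives) gives the primary outcome as "change in carotenoid levels from enrollment to final study visit (birth of child) as measured in serum, skin and the macula". Each tissue has its own instrument, and none is ranked. The objective is "to determine if prenatal supplementation counteracts maternal systemic and ocular carotenoid depletion".

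Study Information, item 9 then adds the following:

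- **Sample Size Calculation and Power Considerations** describes "one of the primary outcome measures, maternal skin carotenoids at birth" and sizes the trial on that outcome alone, at power 0.90 and alpha 0.05. The next paragraph places maternal ocular depletion among the outcomes other than the one just sized, next to infant status and the exploratory measures.
- **Efficacy Analyses:** "Paired t-tests will compare the carotenoid status at enrollment and at the final study visit", set out as a comparison of supplemented with unsupplemented mothers. "Significance will be set at 2-tailed" P < 0.05, with no allocation across outcomes.
- **Subgroup analyses** are to be done "with proper attention to the effects of multiple tests on the ability to draw conclusions". That phrase belongs to the subgroup sentence and names no method.
- **Deferral:** "The complete statistical analysis plan will be finalized prior to database lock, and will provide statistical methods", together with the handling of missing, unused and spurious data. Multiplicity and a success rule are not in that list.

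**The concern.** Three unranked primary tissues with a full 0.05 on each leave the trial's conclusion undefined. A reader cannot tell whether a benefit may be claimed for any tissue that reaches P < 0.05, only for a systemic and an ocular measure together, or only if all three respond.

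These are different trials. Separate claims at 0.05 do not hold a 5% error over the family. Requiring all three holds the error but lowers the chance of success below the stated 0.90. A rule settled after the results are known could not be told apart from one settled before.

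The size of the family is also unclear. Item 6 counts the macula as primary, while the sample size text can be read as setting it apart.

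**Working it through.** **Inputs from the plan.** Skin at birth 34,000, SD 8,300; clinic reference about 42,500; two-sided alpha 0.05; power 0.90; 20 per group for analysis, 30 per group enrolled.

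**Assumptions.** The plan gives no correlation between tissues, so a common correlation r of 0 to 0.9 is used. It gives no effect size for serum or macula on the SD scale, so skin's value is carried over for illustration. The SD of 8,300 is for the level at birth; the SD of change is not given.

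**1. Reproduce the stated sample size.** Difference = 42,500 − 34,000 = 8,500. Standardised effect = 8,500/8,300 = 1.02. Normal approximation: n per group = 2 × (1.960 + 1.282)² / 1.024² = 20.04, in line with the stated 20. At 20 per group, power is 0.899 by the normal approximation and 0.884 by the t-test. So the 20 is what one two-group comparison needs with the whole 0.05 spent on skin.

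**2. Family-wise error if each tissue is claimed separately.** Independent tests: 1 − (1 − 0.05)^k.

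- k = 3: 1 − 0.95³ = 14.3%.
- k = 2 (macula not primary): 1 − 0.95² = 9.75%.

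For correlated tests, two-sample t-tests were simulated at 20 per group with no true difference:

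| r | any of three |
|---|---|
| 0 | 14.3% |
| 0.5 | 12.7% |
| 0.7 | 11.1% |
| 0.9 | 8.4% |

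Repeat simulations agree within a few tenths of a point (8.4–8.7% at r = 0.9). With two tests the range is 9.7% at r = 0 to about 7% at r = 0.9. The error approaches 5% only as r nears 1 (6.0% at r = 0.99).

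**3. Number of serum tests.** The Serum Carotenoid Levels section describes separating all the common carotenoids and names no single serum variable. If lutein and zeaxanthin were tested separately, the family would have four tests: 1 − 0.95⁴ = 18.5% when independent.

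**4. All three required.** The error is at most 5%, so no adjustment is needed. Joint power with 1.02 SD in every tissue:

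| | r = 0 | r = 0.9 |
|---|---|---|
| 20 per group | 69% | 83% |
| 27 per group | 88% | 93% |

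The 27 is 30 × 0.90: enrolment less the plan's roughly 10% ineligibility, with all others analysed. That is an assumption about who stays in the modified intent-to-treat set.

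**5. Skin power under the two candidate procedures, 20 per group, 1.02 SD.** Unadjusted t-test: 88%.

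- **Holm** (thresholds 0.05/3 = 0.0167, then 0.025, then 0.05): 86% at r = 0 to 82% at r = 0.9 if all tissues respond; 77% if only skin does. Simulated family-wise error under the null is 3.1–4.9%.
- **Fixed sequence** skin, serum, macula (each at 1.02 SD, r = 0 to 0.7): skin 88%, serum 78–82%, macula 69–78%.

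At 27 per group, skin power is 96% unadjusted. Under Holm it is 93–95% if all tissues respond and 90% if only skin does.

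**The case against.** **The plan never says that one tissue is enough.** A reader might infer that the trial is declared positive on any single tissue. The text does not say so: the outcome statement is singular, and the objective joins systemic and ocular depletion. This stands, and the 8–14% is therefore conditional on separate claims. The objective still does not settle the rule, because systemic has two measures and each tissue could also be reported on its own.

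**The macula may not be primary.** The sample size text sets maternal ocular depletion apart from skin. It may mean no more than outcomes other than the one just sized, and item 6 names the macula outright. Neither reading can be taken as established. The inconsistency is real, and the two-test range covers the alternative.

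**Within-arm testing.** The name of the t-test might suggest separate before-and-after tests in each arm, and so many more tests. The sentence goes on to compare supplemented with unsupplemented mothers, so one between-group test per tissue is the fair reading and no larger count is claimed.

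**This is only a summary.** The form asks the applicant to "Provide a summary of the statistical methods, data analysis, or data interpretation planned for this study", and a complete SAP is promised before lock. The Background also refers to page numbers of a protocol for its literature list, which suggests a fuller document. This stands as a limit: a rule may exist or be added elsewhere. On the other side, the cover presents these pages as the approved protocol and statistical analysis plan, and the listed contents of the later SAP omit multiplicity.

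**It is Phase II and partly about feasibility.** True, which is why wording is asked for and not more patients. The objective is nevertheless framed as a test, with stated alpha and power.

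**Conclusion.** The point holds in conditional form. As written, the plan puts an unsplit two-sided 0.05 on three unranked primary tissues and states no rule for combining them.

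- **Separate claims:** family-wise error about 14% (independent) to 8–9% (r = 0.9), or about 7–10% if the macula is not primary.
- **All three required:** no inflation, but joint power of 69–83% at 20 per group, reaching 88–93% only if 27 per group are analysed.

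The error figures rest on assumed correlations and one between-group test per tissue. The power figures also rest on 1.02 SD in every tissue, which the plan supports for skin only, and on the SD of the level at birth.

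The documents do not support saying that the trial will certainly exceed 5% error, or that no rule will ever exist. They support saying that none is stated here and that the stated 0.05 does not protect three separate claims.

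**What to change.** Before database lock and unblinding:

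1. **Settle the macula's status.** Confirm whether it is primary, and reconcile Study Purposes and Objectives with the sample size text.
2. **Name one variable per tissue.** Skin is the Raman count. For the macula, the Maternal Macular Pigment Levels section already singles out volume under the curve at 9 degrees as especially reproducible. For serum, choose one, for example lutein plus zeaxanthin.
3. **Replace the unsplit 0.05** for the primary maternal outcomes with one of the following, applied to between-group comparisons of change from enrollment to the final visit:
   - a fixed sequence starting with skin, the sized outcome, at full alpha 0.05; or
   - Holm across the tissues, with a tissue claimed only on its own adjusted result.
4. **If success is meant to require systemic and ocular benefit together,** state exactly which measures must succeed and restate the joint power.

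Report every tissue with its estimate and 95% confidence interval whichever rule is chosen.

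**Cost.** Wording only; no extra patients. Holm at 20 per group lowers skin power from 88% to 82–86% if all tissues respond, and to 77% if only skin does. A fixed sequence costs skin nothing, but tissues after the first non-significant one become descriptive. The choice among these rules belongs to the investigators; what matters is that it is written down before the data are seen.
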